9.5 Serious Adverse Events

Serious adverse events are reported to the sponsor-designated medical monitor using the Aptinyx provided form by email or fax at:

A serious adverse event is any adverse event occurring at any dose that results in any of the following outcomes:

- Death: "Death" is an outcome and is NOT the adverse event. In the event of death, the cause of death should be recorded as the adverse event. The only exception is "sudden death" when the cause is unknown.
- Is a life-threatening experience: Life-threatening adverse events include any adverse drug experience, which, in the view of the investigator, places the subject at immediate risk of death from the reaction as it occurs. It does not include a reaction that, had it occurred in a more serious form, might have caused death.
- Requires inpatient hospitalization or prolongation of existing hospitalization

- Results in a persistent or significant disability/incapacity: Disability is defined as a substantial disruption in a person's ability to conduct normal life functions.
- Results in a congenital anomaly/birth defect
- Additionally, important medical events that may not result in death, be life threatening, or require hospitalization may be considered a serious adverse event when, based upon appropriate medical judgment, they may jeopardize the subject and may require medical or surgical intervention to prevent one of the outcomes listed previously. Example: allergic bronchospasm requiring intensive treatment in an emergency room or at home.

All serious adverse events that result in death or are life threatening, regardless of causal relationship, must be reported to the sponsor-designated medical monitor within 24 hours of the site's knowledge of the event. A copy of the initial serious adverse event report must be received within 1 business day.

All other serious adverse events or other events reportable to the United States Food and Drug Administration (FDA) and/or IRB will be forwarded to the sponsor-designated medical monitor within 1 business day.

The serious adverse event report should provide as much of the required information as is available at the time. The following minimum information is required for reporting a serious adverse event: subject identification, reporting source, and an event outcome. Supplemental information may be transmitted using a follow-up report and should not delay the initial report. Aptinyx may contact the investigational site to solicit additional information or to follow-up on the event.

If there is any doubt whether the information constitutes a serious adverse event, the information will be treated as a serious adverse event for the purposes of this protocol. Serious adverse event reporting will begin at the time of consent and will end 30 days after the last dose.

All relevant documentation pertaining to a serious adverse event (additional laboratory tests, consultation reports, discharge summaries, postmortem reports, etc.) will be provided to the sponsor-designated medical monitor in a timely manner. Serious adverse events will be followed until resolution or return to baseline (when worsening of a pre-existing condition is reported). If a serious adverse event does not return to baseline but reaches a stable situation that is not expected to change, this may be documented on the serious adverse event form.

The Sponsor may break the treatment code for subjects who experience a serious adverse event in order to determine if the individual case or group of cases required expedited regulatory reporting. Individual treatment codes will be available to limited staff who are responsible to break codes for reporting purposes.

All serious adverse events will be reported to the FDA.

9.6 Other Reportable Events

Reports of overdose (with or without an adverse event), abuse, dependency, inadvertent or accidental exposure, pregnancy, and unexpected therapeutic benefit should be forwarded in the same timeframe as a serious adverse event. Overdose occurs when a subject is dosed or has taken

a dose greater than the intended or scheduled dose specified by the protocol. All pregnancies occurring during the study must be followed for information regarding the course of pregnancy, delivery, and condition of the newborn. Follow-up should be provided by the investigator to the sponsor-designated medical monitor in a timely manner. When the newborn is healthy, further follow-up is not necessary. Male subjects must inform the investigator if their partner becomes pregnant during the study. Female subjects of childbearing potential and female partners of male subjects must use an acceptable method of birth control during the participation in this study.

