7 SELECTION AND WITHDRAWAL OF SUBJECTS

7.1 Subject Inclusion Criteria

Inclusion Criteria: Screening

- 1. An IRB-approved written informed consent and privacy language (Health Insurance Portability and Accountability Act) authorization must be obtained from the subject prior to performing any study-related procedures.
- 2. Subjects who consent to being included in a subject registry database.
- 3. Male and female subjects \geq 18 and \leq 75 years of age.
- 4. Subjects with a diagnosis of Type 2 diabetes.
- 5. Subjects with a score of ≥4 and ≤9 on the 11-point NRS for average pain intensity over the past 24 hours at Visit 1.
- 6. Hemoglobin A1c (HbA1c) ≤11% (measured at Visit 1).
- 7. Stable use of diabetic medications beginning 1 month prior to Visit 1. (Adequate glycemic control with only diet and exercise is also permitted).
- 8. Subjects with diabetic peripheral neuropathy, of symmetrical nature and in lower extremities for ≥6 months to ≤10 years, and diagnosed by a score of ≥3 on the Michigan Neuropathy Screening Instrument.
- 9. Body mass index $<40 \text{ kg/m}^2$.
- 10. Calculated creatinine clearance ≥60 mL/minute (Cockcroft-Gault formula).
- 11. Clinical laboratory values must be within normal limits or deemed not clinically significant by the investigator and sponsor-designated medical monitor.
- 12. Female subjects must either:
- Be of non-childbearing potential:
 - Post-menopausal (defined as at least 1 year without any menses) prior to Visit 1;
 or
 - Documented as surgically sterile.
- Or, if of childbearing potential:
 - Agree not to try to become pregnant during the study and for 28 days after the final administration of investigational product;
 - o Have a negative urine pregnancy test at Visit 1; and
 - o If heterosexually active, agree to consistently use 2 forms of highly effective birth control (at least 1 of which must be a barrier method) starting at Visit 1 and continuing throughout the study period and for 28 days after the final administration of investigational product.

- 13. Female subjects must agree not to breastfeed starting at Visit 1 and continuing throughout the study period and for 28 days after the final administration of investigational product.
- 14. Female subjects must not donate ova starting at Visit 1 and continuing throughout the study period and for 28 days after the final administration of investigational product.

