- 15. Male subjects must refrain from sperm donation starting at Visit 1 and continuing throughout the study period and for 90 days after the final administration of investigational product.
- 16. Male subjects who are not surgically sterilized for at least 90 days, and sexually active with a female partner, must use a condom with spermicide during the study, and for 90 days after the last dose of investigational product.
- 17. Has not participated in an interventional study for at least 30 days. Agrees not to participate in another interventional study while on treatment. Eligibility will be reviewed during the study via sponsor participation in a research subject database.
- 18. Ability to understand the requirements of the study, abide by the study restrictions, as well as concomitant medications exclusions, and agree to return for the required assessments.

Inclusion Criteria: Randomization

Daily pain scores and diary compliance will be transferred into the interactive response technology system, which will assess the criteria for randomization. Subjects whose mean of the daily average pain intensity score during the preceding $7 (\pm 1)$ days is within the protocol-defined algorithm and with adequate compliance with daily diary completion will be eligible for randomization.

Waivers to the inclusion criteria will NOT be allowed.

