9.4.2 Recording Adverse Events

A "pre-existing" condition is one that is present before investigational product dosing and is reported as part of the subject's medical history. Pre-existing conditions should be reported as an adverse event only if the frequency, intensity, or character of the pre-existing condition worsens during the course of the study. Adverse events will be collected from the time the informed consent is signed to the end of the subject's participation in the study.

Subjects should be instructed to report all potential adverse events to the investigator, and, queried in a non-leading manner, without specific prompting (e.g., "How are you feeling?"). The site study staff should assess emerging symptoms of dissociative reaction similar to those caused

by NMDA antagonists including memory impairment, disturbance in time, body or environmental perception, stilted speech, emotional withdrawal, impaired coordination, motor retardation, bizarre reasoning or illusory experiences in any sensory perception, or confused state; such symptoms may be captured as adverse events.

To avoid vague, ambiguous, or colloquial expressions, all adverse events should be recorded in standard medical terminology rather than in the subject's own words. Each adverse event will also be described in terms of duration (start and stop date), severity, relationship to investigational product, action(s) taken, and outcome. Diagnoses (rather than symptoms) should be recorded wherever possible.

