10.1 Adverse Events

Treatment-emergent adverse events (TEAEs) will be those occurring during or after administration of the first dose of study drug until 30 days after the final dose of study drug. Due to the nature of this study, the date and time of first dose of study drug was not collected on the CRF. Therefore, the following algorithm will be used to determine if the adverse events are treatment-emergent:

- Earliest Possible AE Start Date ≥ Baseline Visit and Study Drug Dispensation and
- Latest Possible AE Start Date ≤ 30 Days After the Final Dose of Study Drug

Adverse events that started on the Baseline Visit (Study Day 1) that are the result of abnormal clinically significant electrocardiograms (ECGs) or clinical laboratory tests collected prior to study drug dispensation will not be considered TEAEs.

The following System Organ Class (SOC) AEs for abnormal clinically significant clinical laboratory tests will be reviewed to determine if the AE is not treatment-emergent:

- Investigations
- Infections and infestations (with the Preferred Term = "Urinary tract infection")

AEs that started prior to first dosing of study drug, but become worse in severity after receiving study drug will be considered treatment-emergent. The determination of whether or not an adverse event is classified as "treatment emergent" (i.e. TEAE) is not dictated by the classification of "relationship to study drug" collected on the CRF, but rather by the temporal relationship of the adverse event to the administration of study drug.

A related study drug TEAE is defined as any TEAE with at least a possible relationship to the study drug as assessed by the investigator or that is missing the assessment of causal relationship whose relationship to the study drug could not be ruled out. Relationships of "possibly related", "probably related", or missing are collected on the CRF, then those adverse events will be considered related study drug TEAEs. If the "unrelated" or "unlikely related" are collected on the CRF, then those adverse events will be considered not related study drug TEAEs.

Severity is assigned to each adverse event collected on the CRF. Maximum severity has the following order: "life threatening", "severe", "moderate", and "mild" as possible collection options on the CRF. A missing severity will be treated as "unknown" for analysis purposes.

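### Protocol Section 9.6 limits pregnancy capture and partner notification to the study itself, although the protocol's own precautions run 28 days (women) and 90 days (men) past the last dose

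*Protocol*

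**What the plan says.** Section 9.6 of the protocol states: "All pregnancies occurring during the study must be followed", with follow-up extending through delivery to the newborn's condition. For partners it states: "Male subjects must inform the investigator if their partner becomes pregnant during the study". Its closing sentence requires birth control only while the subject is participating. It also says that pregnancy reports are forwarded within the timeframe used for serious adverse events. On those events Section 9.5 says: "Serious adverse event reporting will begin at the time of consent and will end 30 days after the last dose".

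The precautions in Sections 7.1 and 7.5 last longer. Female subjects must avoid pregnancy and use contraception through the study and for 28 days after the last dose. Men who are not surgically sterilized and have a female partner "must use a condom with spermicide during the study, and for 90 days after the last dose of investigational product".

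Section 10.4 places the last visit (Visit 5) 7 days after the Week 4 or Early Termination visit. Table 3 gives it as Day 35 ± 2 and schedules the last pregnancy test at Visit 4.

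At entry, inclusion criterion 12 requires of women of childbearing potential: "Have a negative urine pregnancy test at Visit 1". Table 3 and Section 10.2 repeat the test at Visit 2.

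**The concern.** The period in which a pregnancy must be reported is shorter than the period in which the protocol asks subjects to avoid one. A site that follows Section 9.6 as written need not report a partner's pregnancy that begins in most of the 90-day window. Nor must it report a female subject's pregnancy in most of the 28-day window, unless the timeframe phrase is read as extending the period. Such pregnancies are the ones the precautions are meant to prevent. The Introduction and Section 6.3 describe general toxicology studies and mention no reproductive study, so each exposed pregnancy that reaches the sponsor carries information.

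A second, smaller matter is the Visit 2 test. Exclusion criteria 16 and 21 name Visit 2 for the drug and alcohol screen and for the suicidality scale. No criterion does so for the pregnancy test, so the consequence of a positive result has to be inferred.

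**Working it through.** The plan states no figure on this point, so there is none to reproduce. The check is a comparison of wording followed by day arithmetic.

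**Does the study include the post-dose windows?** Section 6.1 describes a study of 6 to 9 weeks: 1 + 4 + 1 = 6 and 4 + 4 + 1 = 9, counting screening, treatment and one week of follow-up. For a subject, then, the study ends at Visit 5. Criteria 12 and 16 add the 28 and 90 days to the study instead of placing them inside it. Section 9.6 uses the same term without the addition, so on its face it stops at Visit 5.

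**Inputs.** Last dose on Day 28 (assumed: 4 weeks of daily dosing from Day 1). Visit 5 on Day 35, range Day 33 to 37 (Table 3). Windows of 28 and 90 days (Sections 7.1 and 7.5). Reporting period for serious adverse events of 30 days (Section 9.5).

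**Formula.** Window end = 28 + window length. Days after last contact = window end − day of Visit 5.

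| Window | Ends on Day | Days after Visit 5 on Day 35 | Range (Visit 5 on Day 37 to Day 33) | Share of window |
|---|---|---|---|---|
| Female subjects, 28 days | 28 + 28 = 56 | 56 − 35 = 21 | 19 to 23 | 21/28 = 75% |
| Partners of male subjects, 90 days | 28 + 90 = 118 | 118 − 35 = 83 | 81 to 85 | 83/90 = 92% |

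**If the shared timeframe means the 30-day period.** That period ends on Day 28 + 30 = 58. The window for women ends on Day 56, so none of it lies outside. For partners, 118 − 58 = 60 days lie outside, which is 60/90 = 67%.

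**If the shared timeframe means reporting speed** (24 hours or 1 business day, Section 9.5), it does not extend the capture period and the figures in the table stand.

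**Visit 2 pregnancy test, passages side by side.**
- Criterion 12 (Section 7.1) names Visit 1 only.
- Section 6.1 (Baseline) has eligibility re-verified before randomization. It bars subjects with a positive drug or alcohol screen, and beside the pregnancy test it mentions only counseling.
- Section 10.2 lists the pregnancy test before the step at which only subjects who still meet all entry criteria are randomized.
- Section 7.4 lists pregnancy among reasons for which a subject may be withdrawn.
- SAP Section 7.1 lists pregnancy among the CRF reasons for being neither randomized nor treated.

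The documents therefore foresee a consequence, but no entry criterion states it.

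**The case against.** The strongest reply is that a precaution window and a reporting window serve different purposes and need not be equal. That is a tenable design choice in general. It does not explain why Section 9.6 also shortens the birth-control requirement itself, which conflicts with Sections 7.1 and 7.5, or why the phrase that decides the reporting period can be read two ways.

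Other points stand in part. Having no scheduled contact is not the same as having no reporting: subjects are told to report adverse events, and reporting of serious events stays open for 30 days. A reporting instruction might also appear in the consent form, which is not available here. SAP Section 5.8 notes that most enrolled subjects are at least 45, and the documents give no expected number of pregnancies, so the number affected may be small.

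Four stronger readings are tempting, and the documents do not support them.
- *Pregnancy follow-up stops when the study stops.* It does not. A captured pregnancy is followed through delivery to the condition of the newborn.
- *The 30 days is a third reproductive-risk window.* It is the reporting period for serious adverse events.
- *A positive Visit 2 test has no effect on eligibility.* Sections 6.1 and 10.2 re-verify eligibility before randomization, and the SAP records pregnancy as a reason for non-randomization. The permissive verb in Section 7.4 proves little: the same list includes the stopping criteria, which Section 11 makes mandatory.
- *The SAP's window for treatment-emergent events is wrong*, because Section 9.4.2 says "Adverse events will be collected from the time the informed consent is signed to the end of the subject's participation in the study" while SAP Section 10.1 counts events to "30 days after the final dose of study drug". The SAP limit only classifies events that were recorded, and SAP Section 5.4.1 allows repeat follow-up visits after Visit 5. It gives no wrong result and needs no change.

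**Conclusion.** The concern holds for the capture window. As worded, Section 9.6 covers only the study, while the protocol's own precautions run 28 and 90 days past the last dose. With the last dose on Day 28 and Visit 5 on Day 35, 21 of 28 days for women and 83 of 90 days for partners fall after the last scheduled contact. Under the reading most favorable to the plan, the gap for women is zero and that for partners is 60 of 90 days. The partner gap therefore remains on either reading, and the gap for women depends on an ambiguous phrase.

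These figures are days without scheduled contact or a clear reporting duty, not expected pregnancies. For early terminators Visit 5 is counted from the termination visit, which may fall some days after the last dose; the gaps are then shorter by that delay.

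The consequence of a positive Visit 2 test is a matter of clarity only. Neither matter touches the efficacy analysis. This is an inexpensive improvement to safety reporting.

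**What to change.** In Section 9.6:
- Let pregnancy reporting and partner notification run to the end of the post-dose windows already set in Sections 7.1 and 7.5, by reference to those sections.
- Reconcile the birth-control sentence with the same sections, so that the protocol states one period.
- State whether the timeframe shared with serious adverse events means speed of reporting or the 30-day period.
- Have the site give subjects the reporting instruction at Visit 5.

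Separately, reconcile Protocol Sections 6.1, 7.1, 7.4 and 10.2 with SAP Section 7.1 on what follows a positive Visit 2 pregnancy test. The rule itself is for the sponsor and investigators to set.

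The cost is a wording amendment and a short instruction at a visit that already takes place. No added visit or telephone call is needed. The downside is passive reporting for some weeks after Visit 5: about 3 weeks for women (21 days) and about 12 weeks for partners (83 days).

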10 SCHEDULE OF PROCEDURES

The schedule of procedures is summarized in Table 3.

10.1 Screening Period (Week -4 to -1)

The subject will be asked to provide informed consent for this study before any required procedures are performed. Subjects will also be asked to sign an additional consent for their inclusion in a subject registry database. Adverse event collection will begin at the time of informed consent.

After the informed consents are signed, the following procedures and assessments should be completed at Visit 1:

- Confirmation of diabetic peripheral neuropathy by the following assessments:
 - Michigan Neuropathy Screening Instrument
 - o Masquerading Disorders Tool
 - o American College of Rheumatology Fibromyalgia Criteria
- NRS for average pain intensity over the past 24 hours
- Demographic characteristics (age, sex, race, and ethnicity)
- Medical history
- Prior (within last 30 days) and concomitant medications
- Height and body weight
- Sitting vital signs (blood pressure and pulse after 5 minutes)
- Complete physical examination, including comprehensive neurological examination
- Electrocardiogram after 5 minutes in supine position
- Urine pregnancy test for females of childbearing potential
- Urine drug test
- Breathalyzer test for alcohol
- Blood samples for fasting (8 hours) serum chemistry HIV, hepatitis B surface antigen, hepatitis C antibody, triglycerides, and hematology (including HbA1c)
- Urine sample for urinalysis
- HADS
- S-STS
- Adverse events

Eligible subjects who meet all inclusion and exclusion criteria will enter the 1- to 4-week Screening Period. The following procedures and assessments will be performed:

- Subjects who are taking more than 1 analgesic medication will discontinue all but 1 of the medications as allowed by the protocol before the start of daily pain and sleep evaluations. The duration of their Screening Period will depend on the time required to discontinue analgesic medications, but the total duration of the Screening Period cannot exceed 4 weeks. Subjects who are taking no more than 1 allowed analgesic medication will begin daily pain and sleep evaluations at bedtime immediately after Visit 1 (i.e., will begin Week -1).
- Subjects will be provided a handheld device, and as a method for ensuring consistency and reliability of pain scoring, instructed on how to record their pain on the device

 Subjects will also be educated on appropriate expectations around their participation in a clinical study

 On each of the days preceding Visit 2 (Baseline Visit), subjects will record the following on the handheld device:
 - O At bedtime: average pain intensity, worst pain intensity, pain on walking, and use of rescue medication during the past 24 hours
 - Upon waking: DSIS
- Subjects will be dispensed acetaminophen to be used as rescue medication, and will be instructed to take no more than 2 g/daily (one to two 500-mg caplets every 4 to 6 hours as needed) for DPN pain.
- The investigative site staff will contact study subjects by telephone weekly until and including Week -1 to reinforce the reporting instructions (7±2 days prior to Visit 2) and assess adverse events.

